Specific Aim 2: To conduct candidate biomarker investigations quantifying pregnenolone and pregnenolone metabolite levels (allopregnanolone, pregnanolone, androsterone, others) in serum samples at baseline, during treatment, and post-treatment with pregnenolone using mass spectrometry-based technologies, and to investigate potential genetic predictors of therapeutic response. These investigations will thus: a.) characterize the pharmacokinetics of pregnenolone and its metabolic profile - which could yield valuable dosing information for pregnenolone, characterize pharmacological windows of optimal therapeutic efficacy, and identify potential neurosteroid predictors of therapeutic response, and b.) examine single nucleotide polymorphisms (SNPs) of genes coding for enzymes involved in neurosteroid synthesis and metabolism. *Together these studies could contribute to the development of new neurosteroid interventional strategies that build on the current investigation and exhibit promise as pharmacological candidates in GWVI.* Based on our preliminary candidate biomarker data that neurosteroids are altered in CNS disorders (Marx et al 2006a, Marx et al 2006b, Marx et al 2006c, Naylor et al 2008, Naylor et al 2010, Kilts et al 2010), and that neurosteroid alterations following treatment with pregnenolone may be associated with therapeutic response (Marx et al 2009), we hypothesize that changes in pregnenolone levels (and pregnenolone metabolite levels) post-treatment will predict therapeutic response to this intervention. We also hypothesize that neurosteroids are dysregulated in GWVI, and that specific SNPs of genes coding for neurosteroidogenic enzymes will be associated with therapeutic response. Additionally, we hypothesize that changes in one or more pregnenolone metabolites may also predict therapeutic response, and potentially lead to the identification of additional neurosteroid targets that demonstrate promise for treating diverse symptoms impacting functional outcome and quality of life in Gulf War Veterans with GWVI.

SUBJECT RECRUITMENT

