Pregnenolone 500 mg in divided doses (250 mg BID) for 4 weeks.

Compliance with study drug treatment will be assessed by counting the returned study drug supply. Subjects that fall below 80% compliance at 2 consecutive visits or miss 6 consecutive doses in a row (3 days of study drug) for two consecutive visits should be withdrawn from the study.

Study Timeline:

1. Referred patients and patients responding to IRB-approved advertisements and/or IRB-approved letters with follow-up phone calls (using an IRB-approved phone script) will meet with a member of the research team to discuss the study and the risks and benefits of participation. In addition, patients will be screened for exclusion and inclusion criteria. If subjects are interested in potentially participating in the study, the informed consent document will be discussed with them. Patients will have the option of taking the informed consent with them and discussing the matter with family, friends and/or clinicians. If applicable, the participant's physician or other VA provider will be consulted regarding the patient's appropriateness of the patient's enrollment in the study.
2. Once the informed consent is signed, the subject will proceed to the initial screening procedures. Each participant will receive the MINI diagnostic assessment tool (Mini-International Neuropsychiatric Interview).
3. A licensed physician, nurse practitioner (NP), or physician's assistant (PA) who is clinically privileged at the Durham VA will examine patients prior to randomization to study drug (pregnenolone) or placebo. Patients will have a venous puncture for laboratory/genetic testing (please also the Schedule of Events). Patients will be asked to provide approximately 3.5 tablespoons of blood on the first study visit, and approximately 2.5 tablespoons of blood on Visits #2, 3, 4, 5, 6 and 7. This is a total of approximately 16 tablespoons of blood over the duration of the study. Subjects will receive an ECG at Visits #1 and 6. Patients with clinically significant abnormal physical exam, blood tests, or ECG that preclude safe study participation will be excluded from the study and referred to their primary care provider or appropriate specialist.

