4. Following the screening visit (Visit 1), all patients will begin a two-week placebo-only lead-in period (prior to randomization at Visit 2). On the day that patients are given the study medication and randomized (and at each visit during the study), a set of vital signs will be done including pulse, blood pressure, and weight. With regard to the study medication, participants will be told that they could be getting placebo (a sugar pill) or active medication (pregnenolone). The subjects will be told that they may be receiving a different dose every two weeks. They will be asked to take the medication twice a day; once in the morning and once in the evening.
5. After a week of the placebo lead-in period, a member of the research team will contact the participant to ask about study medication compliance and to answer any questions. A member of the research team will continue to contact patients by phone every two weeks to ask about compliance to study medication, possible suicidality, and potential adverse events (these telephone check-in contacts will be staggered with in-person patient visits every two weeks; please see also Schedule of Events for details).
6. Subjects will return for a study visit every two weeks. Vital signs will be repeated at each visit. A member of the research team will ask subjects about possible side effects and adverse events (utilizing a structured Adverse Event

Form) and will administer the Columbia Suicide Severity Scale to assess possible suicidality. Patients will be asked to return tablets of pregnenolone or placebo to determine compliance with study medication by pill counting. The subject will be given a new supply of tablets (either pregnenolone or placebo, depending upon random assignment) every two weeks. Patients will receive a laboratory testing (Chem 7, GI panel, CBC) at all study visits. Female patients will also receive a pregnancy test at Visits #1, 2, 4 and 6. TSH, free T4, B12/folate, and a lipid panel will be assessed at Visits #1 and 6. A urinalysis and urine tox screen will be conducted at Visits 1, 2, 4, and 6.

7. At Visits #1 (screening visit), 2 (randomization visit), 3, 4, 5 and 6 (each visit is 2 weeks apart), three extra red-top tubes will be collected for pregnenolone levels and determination of pregnenolone metabolite levels, proteins, and other small molecules. A PaxGene tube and two purple top tubes will be collected at Visit #1 (for genetic analyses).

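### Aim 2's pharmacokinetic and efficacy-window wording goes beyond what one sample per visit, no stated time since dose and a single forced titration can support

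*Combined protocol and SAP*

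**What the plan says.** Specific Aim 2, under Research Design and Methods and again in the statistical section after the power analyses, says the serum studies will "characterize the pharmacokinetics of pregnenolone and its metabolic profile - which could yield valuable dosing information for pregnenolone". The same sentence goes on to "characterize pharmacological windows of optimal therapeutic efficacy". The pharmacokinetic objective is stated flatly. The dosing benefit is hedged with a conditional, which can be read as covering the windows too. The aim's leading hypothesis is that changes in pregnenolone and metabolite levels will predict response.

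The means provided are these:

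- **Sampling.** Study Timeline, item 7: at each of Visits 1 to 6, "three extra red-top tubes will be collected for pregnenolone levels and determination of pregnenolone metabolite levels, proteins, and other small molecules". The spacing is "3, 4, 5 and 6 (each visit is 2 weeks apart". No neurosteroid tubes are listed for the follow-up visit.
- **Dosing.** Study Timeline, item 4: medication is taken "once in the morning and once in the evening". Nothing in the text reviewed ties the draw to a dose or asks for the time of either. Compliance is checked by pill count and telephone contact.
- **Titration.** Under Pregnenolone: 50 mg BID for 2 weeks, 150 mg BID for 2 weeks, then "Pregnenolone 500 mg in divided doses (250 mg BID) for 4 weeks". There is one active regimen.
- **Outcomes.** Study Timeline, item 9: SF-36 and the other efficacy scales at Visits 2, 4 and 6 (Weeks 0, 4 and 8).
- **Analysis.** The Statistical Analysis Plan describes a general repeated-measures mixed model. It contains no pharmacokinetic, exposure-response or dose-response model.

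The Study Timeline refers to a Schedule of Events, which is not in the text reviewed.

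**The concern.** Two separate problems sit in one sentence of the aim.

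The first is time since dose. A single level at an unknown point in a roughly 12-hour interval mixes a person's exposure with the hour of the clinic slot. That blocks most pharmacokinetic parameters. It also puts measurement error into the predictor of the level-response hypothesis, so a null result there could be partly a sampling artefact. The plan takes care over smaller error sources: it quotes intra-assay coefficients of variation of 1.5-8.0% and batches the assays after study completion to limit inter-assay variation. Because levels are run only then, a last-dose time not written down at the visit may not be recoverable.

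The second is dose. Everyone on active drug moves through the same steps in the same weeks, so the data cannot say whether a later change reflects a higher dose or longer treatment. Dosing conclusions would have no design behind them.

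**Working it through.** Aim 2 states no sample size, precision or pharmacokinetic figure, so there is nothing to reproduce first.

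**1. What is sampled on drug (from the titration and Study Timeline)**

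| Visit | Week | Step just completed | Level | Efficacy scales |
|---|---|---|---|---|
| 3 | 2 | 50 mg BID | one | no |
| 4 | 4 | 150 mg BID | one | yes |
| 5 | 6 | 250 mg BID | one | no |
| 6 | 8 | 250 mg BID | one | yes |

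That is four on-drug levels per participant. The taper begins at Visit 6, so no listed level falls in washout.

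**2. Pharmacokinetic parameters**

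Assume a linear one-compartment oral model at steady state. Then log C(t, D) = log D + f(t; CL/F, V/F, ka). Changing the dose only adds a known constant. If t is unknown, the mean levels inform only the average of f, which is one quantity for three parameters. A numerical check agreed: the sensitivity matrix of mean log-level over the dose steps had rank 1 for assumed half-lives of 3, 6 and 12 h.

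With recorded times, the same four samples would give these relative standard errors. Assumptions: 70 active participants, V/F 100 L, ka 1 per h, log residual SD 0.5, draws uniform over 1-8 h after dose. There is no endogenous baseline and no separate between-subject variance, so the figures are optimistic.

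| Half-life | CL/F | V/F | ka |
|---|---|---|---|
| 3 h | 4.0% | 14.7% | 31.8% |
| 6 h | 4.7% | 25.2% | 43.2% |
| 12 h | 4.8% | 48.2% | 67.3% |

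**3. Noise in the level-response analysis**

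The documents give no half-life, so a range is assumed. Assume also mono-exponential decline, draws uniform over 1-8 h, and a true between-person SD of 0.4 on the log scale (variance 0.16).

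- Range of level from timing alone = 2^(7 / half-life).
- SD of log-level from timing, s = (ln 2 / half-life) × 7 / √12.
- Reliability = 0.16 / (0.16 + s²). The observed correlation is the true one times the square root of reliability.
- If the Visit 5 and 6 levels are averaged and their draw times are independent, s² is halved.

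| Half-life | Range | s | Reliability, one sample | Correlation kept | Reliability, V5-V6 mean | Correlation kept |
|---|---|---|---|---|---|---|
| 3 h | 5.04-fold | 0.467 | 0.16/(0.16+0.218) = 0.42 | 65% | 0.16/(0.16+0.109) = 0.59 | 77% |
| 6 h | 2.24-fold | 0.233 | 0.16/(0.16+0.054) = 0.75 | 86% | 0.16/(0.16+0.027) = 0.85 | 92% |
| 12 h | 1.50-fold | 0.117 | 0.16/(0.16+0.014) = 0.92 | 96% | 0.16/(0.16+0.007) = 0.96 | 98% |

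**4. Dose against time on treatment**

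At the three efficacy visits the active arm's daily dose is 0, 300 and 500 mg at Weeks 0, 4 and 8. Deviations from the means are -266.7, 33.3, 233.3 and -4, 0, 4. The cross-product is 1066.7 + 0 + 933.3 = 2000. The sums of squares are 126,667 and 32. The correlation is 2000 / √(126,667 × 32) = 0.99. More to the point, each dose occurs at one efficacy week only, so no participant supplies a contrast of dose at fixed time.

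**The case against.** Several stronger conclusions are tempting, and the documents do not support them.

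- **That no pharmacokinetic information can be derived.** Even without times, the samples give mean level at each step, the rise over baseline and over placebo, metabolite-to-parent ratios and a crude average exposure. If times are known, a sparse-sample analysis could estimate CL/F usefully.
- **That the draws are untimed.** This is an inference from silence. The Schedule of Events could hold timing detail.
- **That levels from different people or visits are not comparable.** The reliabilities of 0.75 and 0.92 at half-lives of 6 and 12 h contradict this. They are less comparable, and seriously so only if the half-life is short.
- **That no efficacy window of any kind can be examined.** The aim concerns serum levels, and a concentration window can be explored among participants at the same dose, for example at Week 8. That comparison is not randomised, but dose-time confounding does not enter it.
- **That the trial's main result is at risk.** This is a candidate-biomarker aim, and the Aim 1 endpoints are untouched.

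It is also fair to say that a forced titration is a legitimate choice in a two-arm efficacy trial. The attenuation figures rest on assumed inputs and describe a mono-exponential parent drug; no equivalent is shown for metabolites.

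All of this stands, and it narrows the point. It does not supply a pharmacokinetic or exposure-response model, and nothing in a visit schedule could separate dose from week. The placebo arm removes time trends common to both arms, but not the overlap of 300 versus 500 mg with 4 versus 8 weeks of treatment.

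**Conclusion.** The concern holds in a limited form. On the text reviewed, the parameters that depend on the shape of the concentration curve (half-life, Cmax, tmax, within-interval AUC, V/F and ka) are out of reach; descriptive levels are not. This part is conditional on the Schedule of Events adding no timing record.

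The loss in the level-response analysis runs from slight to material: 4% to 35% of the true correlation for one sample, and 2% to 23% if the two 500 mg levels are averaged. Half-life, draw spread and between-person SD are assumptions. At half-lives of 6-12 h the single-sample loss is only 4-14%.

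The dose-window conclusion needs no such assumption. It follows from the single titration and the three outcome visits, and it stands whatever the Schedule of Events contains. The point merits action because the timing data are cheap to collect during the trial and hard to recover afterwards.

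**What to change.** 1. Unless the Schedule of Events already does so, record the clock time of the last dose and of each neurosteroid draw at Visits 3 to 6, in both arms so that the blind is undisturbed. Use time since dose as a covariate in level-based analyses. Then choose one of two courses. If the pharmacokinetic wording is kept, pre-specify a sparse-sample population model that uses these times. If not, reword that part of Aim 2, in both places where it appears, as a description of serum pregnenolone and metabolite levels at each titration step.
2. In either case, state in Aim 2 and the Statistical Analysis Plan that dose and time on treatment are confounded, that no dose-response or dose-window conclusion will be drawn, and that concentration-response analyses are exploratory.

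The cost is two fields on the visit form and a narrower stated aim, plus some modelling work if the pharmacokinetic wording is kept. No extra blood, visits or participants are needed.

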The Institute of Medicine Committee on Gulf War and Health also notes that "*inadequate numbers of clinical trials have been undertaken to develop more effective and evidence-based treatments for multi-system illness,*" and calls for "a renewed research effort to identify and treat multi-system illness in Gulf War Veterans." The IOM Committee also states that it is "*optimistic that a rigorous, adequately powered study could identify useful biomarkers that are helpful for symptomatic Veterans of the Gulf War and for non-deployed Veterans and civilians who have a variety of medically unexplained symptoms, including chronic fatigue, muscle and joint pain, sleep disturbance, difficulty with concentration, and depression*" (IOM Update 2009). The current proposal investigating a novel complementary neurosteroid intervention in Gulf War Veterans with GWVI and candidate biomarkers of therapeutic response is thus clearly aligned with this Institute of Medicine mandate. The rationale for utilizing a neurosteroid intervention in Gulf War Veterans with GWVI is outlined below.

RESEARCH DESIGN AND METHODS

Specific Aim 1: To conduct an RCT with the neurosteroid pregnenolone in 140 Gulf War Veterans with GWVI and a history of deployment (70 Veterans randomized to adjunctive pregnenolone, 70 Veterans randomized to placebo), targeting functional outcome as the primary endpoint (as assessed by the SF-36). Secondary endpoints will be pain symptoms, cognitive symptoms, fatigue, and global psychological functioning. ***Based on our preliminary data from multiple investigations, we hypothesize that adjunctive pregnenolone will significantly improve functional outcomes, pain symptoms, cognitive symptoms, fatigue, and global psychological symptoms in Gulf War Veterans with GWVI.***

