We propose to conduct a randomized controlled trial (RCT) investigating a novel neurosteroid intervention in Gulf War Veterans with GWVI. Research participants will be recruited via Durham VA IRB-approved local advertising (flyers), Durham VA IRB-approved letters (and follow-up phone calls utilizing a Durham VA IRB-approved phone script), Vet Centers, and the VISN 6 MIRECC Post-Deployment Mental Health Data Repository (over 95% of these Registry participants have provided permission to be re-contacted for future research studies; over a quarter of Veterans in this OEF/OIF/OND era Registry are also Gulf War era Veterans), and by referral from the Durham VA, Raleigh CBOC, Greensboro CBOC, and Morehead City CBOC medical and behavioral health care providers. The target number of participants for this study is 140 subjects who complete at least 4 weeks of the study post-randomization (70 subjects per group, randomized to either adjunctive pregnenolone or placebo). Based on our prior investigations with pregnenolone, we conservatively estimate a drop-out rate of 30%. The power analysis for this study in GWVI was conducted under the assumption that 140 participants reach Visit 4 of the study (i.e. 4 weeks post-randomization). With an estimated 30% drop-out rate, we thus anticipate that we will have to randomize approximately 200 participants to achieve this goal.

Enrolled subjects will be 1). Veterans deployed to the Gulf War theater of operations between 1990 and 1991, 2). Gulf War Veterans who report at least 2 of the following 3 symptoms that began in 1990 or thereafter, that have lasted for more than 6 months, and that are present at the time of screening: a) fatigue that limited usual activity, b) musculoskeletal pain involving 2 or more regions of the body, c) cognitive symptoms (memory, concentration, or attentional difficulties by self-report, 3) on a stable medication regimen (no change in past 4 weeks) and no anticipated change in medications during study, 4) Able to provide informed consent for study participation. Only Gulf War era Veterans will be enrolled into this study. There will be no non-Veteran participants enrolled in this study.

RECRUITMENT PROCEDURES

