We will assess this hypothesis in the context of a two factor repeated measures mixed model ANOVA, with one between subjects factor with two levels (pregnenolone vs. placebo) and one within subjects factor with three levels (Weeks 0, 4, 8 of treatment post-randomization, which correspond to Visits 2, 4, and 6). This hypothesis will be tested using the treatment-by-time interaction, followed by contrasts in least squares means. These contrasts will examine the difference between the treatments at Weeks 4 and 8 on the changes between least squares means between Week 0 to Week 4, and Week 0 to Week 8 of treatment post-randomization. We will perform several such analyses, one for functional outcome as assessed by the Physical Component of the SF-36 (primary endpoint), and others for secondary endpoints, including: pain symptoms (as assessed by the Brief Pain Inventory), executive functioning (as assessed by the Tower of London test of the BACS), fatigue (as assessed by the Multidimensional Fatigue Inventory), and overall psychological functioning (as assessed by the Global Severity Index of the SCL-90R). The response variable will be change from baseline, and we will use baseline as a covariate. Exploratory outcomes will include the BACS composite score (cognitive symptoms), resilience (as assessed by the Connor-Davidson Resilience Scale), anxiety and depression symptoms (as assessed by the Hospital Anxiety and Depression Scale), PTSD symptoms (as assessed by the PTSD Symptom Checklist), and depression symptoms (as assessed by the Beck Depression Inventory-II scale).

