3. This project will involve independent PhD-level statisticians. [name] will be completely removed from the conduction of the statistical analyses. After clinical trial data are entered by research staff, double-checked, and cleaned, the database will be locked. No statistical analyses will be conducted prior to the locking of the database. Once the data are locked, a completely de-identified copy of the dataset (no PHI) will be sent to independent statisticians. Once the de-identified database is locked, the blind will then be broken by pharmacist [name]. [name] will conduct the statistical analyses (the statistical analysis plan will be determined a priori), and this analysis will be confirmed by an independent statistician.
4. There will be a VA DSMB that will be overseeing this project.
5. [name] will promptly contact the Durham VA IRB Committee, the Durham VA R+D Committee, the VA DSMB, and the ACOS for Research at the Durham VA if a patent is issued or if a licensing agreement is negotiated.

POWER ANALYSIS: PHYSICAL COMPONENT OF THE SF-36 (Primary Endpoint).

Primary Endpoint Hypothesis: Gulf War Veterans with GWVI who were randomized to pregnenolone will demonstrate significantly greater improvements in the Physical Component Score of the SF-36 compared to Veterans randomized to placebo.

Numeric Results for Two-Sample T-Test

Null Hypothesis: Mean1=Mean2. Alternative Hypothesis: Mean1 > Mean2

The standard deviations were assumed to be equal. A prior investigation in Gulf War Veterans with GWVI determined mean baseline standard deviation in the SF-36 Physical Component Summary to be 7.5 (Donta et al 2003). We chose a more conservative SD estimate of 12.5 for this sample calculation. We utilized the baseline SF-36 score from the same investigation (Donta et al 2003) to estimate approximate baseline SF-36 scores in a Gulf War Veteran cohort with GWVI. Consistent with the literature in this area, we utilized a 7-point difference in the SF-36 as a clinically meaningful change from baseline for this sample size calculation (please see attached SF-36 scoring information in Appendix).

[figure not shown]
Power	Allocation		Alpha	Beta	Mean1	Mean2	S1	S2
	N1	N2						
0.71774	42	42	0.05000	0.28226	33.7	40.7	12.5	12.5
0.75708	46	46	0.05000	0.24292	33.7	40.7	12.5	12.5
0.79175	50	50	0.05000	0.20825	33.7	40.7	12.5	12.5
0.82211	54	54	0.05000	0.17789	33.7	40.7	12.5	12.5
0.84855	58	58	0.05000	0.15145	33.7	40.7	12.5	12.5

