0.87147	62	62	0.05000	0.12853	33.7	40.7	12.5	12.5
0.89124	66	66	0.05000	0.10876	33.7	40.7	12.5	12.5
0.90822	70	70	0.05000	0.09178	33.7	40.7	12.5	12.5
0.92276	74	74	0.05000	0.07724	33.7	40.7	12.5	12.5
0.93516	78	78	0.05000	0.06484	33.7	40.7	12.5	12.5
0.94569	82	82	0.05000	0.05431	33.7	40.7	12.5	12.5

Report Definitions

- Power is the probability of rejecting a false null hypothesis. Power should be close to one.
- N1 and N2 are the number of items sampled from each population; they should be small.
- Alpha is the probability of rejecting a true null hypothesis. It should be small.
- Beta is the probability of accepting a false null hypothesis. It should be small.
- Mean1 is the mean of populations 1 and 2 under the null hypothesis of equality.
- Mean2 is the mean of population 2 under the alternative hypothesis. Mean of population 1 is unchanged.
- S1 and S2 are the population standard deviations. They represent the variability in the populations.

Summary Statement

Group sample sizes of 70 and 70 will **achieve 90% power to detect a difference of 7 points** between the null hypothesis that both group means are 33.7 and the alternative hypothesis that mean of Group 2 is 40.7 with estimated standard deviations of 12.5 and 12.5 and with a significance level (alpha) of 0.05000 using a two-sided two-sample t-test. We thus have 90% power to detect a 7-point improvement in the SF-36.

POWER ANALYSIS: PAIN SYMPTOMS (Secondary Endpoint)

[figure not shown]
Secondary Hypothesis #1: Treatment with pregnenolone will improve pain symptoms in Gulf War Veterans with GWVI.

The potential effect of pregnenolone on pain symptoms will be evaluated using several statistical methods. This clinical trial design will compare two randomly assigned groups (adjunctive pregnenolone or placebo) with respect to self-reported pain measured on a 1-10 pain scale. Inclusion criteria for the study require that all participants report pain severity of at least four. Given that pain often presents as long periods of low-level intensity pain punctuated by periods of acute exacerbation, it is likely that the mean pain level for selected participants will exceed four. Thus for power calculations, we assume a baseline mean pain level of six for each group. We assume a standard deviation of 1.0 (as we have little information to support any specific value in this population).

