For the purpose of power calculations we assume that the mean pain levels of the two independent groups will be compared using a Two-Sample T-Test, Null Hypothesis: Mean1=Mean2. Alternative Hypothesis: Mean1 > Mean2. The standard deviations were assumed to be unknown and equal.

Assuming specified numbers of participants in each group (N) the mean differences detectable for at least 80% power and alpha=0.05 are shown in the following table and figure.

N1	Mean1	Mean2
4	6.0	3.6
5	6.0	3.8
6	6.0	4.0
6	6.0	4.2
8	6.0	4.4
10	6.0	4.6
12	6.0	4.8
17	6.0	5.0
26	6.0	5.2
45	6.0	5.4
100	6.0	5.6

Group sample sizes of 45 achieve at least 80% power to detect a difference of 0.6 between the null hypothesis that both group means are 6.0 and the alternative hypothesis that the mean of group 2 is 5.4 with estimated group standard deviations of 1.0 and 1.0 and with a significance level (alpha) of 0.05 using a two-sided two-sample t-test. We will have 70 Veterans per group, and should thus have **94% power to detect a difference in pain symptoms of 0.6** in the pregnenolone intervention compared to placebo.

POWER ANALYSIS: COGNITIVE SYMPTOMS (Secondary Endpoint)

Executive functioning as assessed by the Tower of London Test of the BACS cognitive assessment battery, Keefe et al.

The Tower of London component of the BACS cognitive assessment battery demonstrated improvements in the hypothesized direction in two of our prior pilot RCTs in Veterans with schizophrenia and mild TBI who had been randomized to pregnenolone (moderate effect sizes). We thus did power and sample size calculations for Tower of London executive functioning scores (secondary cognitive outcome measure) from estimates of means and standard deviations (SD) from preliminary data derived from our pilot RCT examining pregnenolone in OEF/OIF era Veterans with mild TBI. We conservatively utilized our pilot RCT in Veterans with TBI rather than our pilot RCT in Veterans with schizophrenia, as Veterans with schizophrenia demonstrated somewhat greater mean improvements in the Tower of London test (z-score change 0.61 greater than placebo). We used simplified models on change scores for power calculations as we do not know, and cannot reasonably estimate, the covariance parameters we would need to do these calculations in the context of the mixed models. We used correlations of 0.50 between all occasions, which is probably a conservative estimate (please see attached scoring information for BACS in Appendix).

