[figure not shown]
Secondary Hypothesis #2: Treatment with pregnenolone will improve executive functioning in Gulf War Veterans with GWVI, as assessed by the Tower of London test of the BACS.

Our preliminary data from our pilot RCT utilizing adjunctive pregnenolone in Veterans with mild TBI showed two estimates of standard deviation of change scores of 0.7546 in the placebo group and 0.9238 in the pregnenolone group. Our power analysis assumed a standard deviation consisting of the mean of these two groups = 0.8392, or approximately 0.84. Our preliminary data from our pilot RCT utilizing pregnenolone in OEF/OIF Veterans with mild TBI showed a difference between treatment and placebo of 0.435, or approximately 0.44. We did calculations for treatment differences ranging from 0.30 to 0.55 in the table below. To have 80% power to detect a difference of 0.44 between treatments (the difference in z-scores observed in Tower of London executive functioning scores in the pregnenolone group compared to the placebo group in our pilot RCT), we would require 61 subjects per group, or 122 subjects total. This may be a conservative estimate in that this assumes a correlation of 0.50 between baseline and endpoint, and the correlation is likely to be higher, and the mixed model is likely to have more power than the simpler model we used here. We will, however, have 70 subjects per group in the current investigation (in order to achieve 91% power for the primary hypothesis – that Veterans randomized to adjunctive pregnenolone will demonstrate significantly greater improvements in the SF-36 compared to Veterans receiving placebo), which will provide 86% power to detect a z-score change of 0.44 with a standard deviation of 0.84 for Secondary Hypothesis #1 as shown in the table and figure below:

Secondary Hypothesis #2: Tower of London Test of Executive Functioning

Power	N1	N2	Alpha	Beta	Mean Diff	Std Dev
0.559763	70	70	0.050000	0.440237	0.30	0.84
0.692311	70	70	0.050000	0.307689	0.35	0.84
0.803596	70	70	0.050000	0.196404	0.40	0.84
0.864561	70	70	0.050000	0.135439	0.44	0.84
0.886225	70	70	0.050000	0.113775	0.45	0.84
0.940490	70	70	0.050000	0.059510	0.50	0.84

0.972010 70 70 0.050000 0.027990 0.55 0.84

Summary Statement: 70 subjects per group will provide **86% power to test Secondary Hypothesis #2** that treatment with pregnenolone will improve executive functioning as assessed by the Tower of London test compared to placebo in Gulf War Veterans with GWVI.

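### Does Aim 1's count of 140 randomised, against about 200 in Subject Recruitment, undermine the stated 90% power?

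*Combined protocol and SAP*

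**What the plan says.** - **Number randomised.** Specific Aim 1 (Research Design and Methods) describes a trial in 140 Veterans: "70 Veterans randomized to adjunctive pregnenolone, 70 Veterans randomized to placebo". Subject Recruitment sets the target as 140 participants, 70 per group, who complete at least four weeks after randomisation. It estimates drop-out at 30% and concludes: "With an estimated 30% drop-out rate, we thus anticipate that we will have to randomize approximately 200 participants to achieve this goal".
- **What the power refers to.** Subject Recruitment states: "The power analysis for this study in GWVI was conducted under the assumption that 140 participants reach Visit 4 of the study".
- **Primary endpoint power.** The power section for the SF-36 Physical Component uses group means of 33.7 and 40.7 and a two-sided alpha of 0.05. On the SD, where a prior study gave 7.5, it says: "We chose a more conservative SD estimate of 12.5 for this sample calculation". At 70 per arm the table gives 0.90822. The summary ends: "We thus have 90% power to detect a 7-point improvement in the SF-36".
- **Secondary endpoints.** The pain section says "We will have 70 Veterans per group, and should thus have" 94% power. The Tower of London section says "We will, however, have 70 subjects per group in the current investigation" and states 86%.
- **Analysis.** Study Interventions plans a repeated measures mixed model over Weeks 0, 4 and 8 with baseline as a covariate. The treatment-by-time interaction is tested first, then contrasts: "These contrasts will examine the difference between the treatments at Weeks 4 and 8". The Statistical Analysis Plan defaults to an AR(1) covariance and relies on the mixed model under missing at random. No section gives a loss rate between Week 4 and Week 8.

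**The concern.** Three things look wrong on a first reading.

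1. Aim 1 and Subject Recruitment both speak of randomising, but one says 140 and the other about 200. The figure of 200 appears only once, and the power sections repeat 70 per group without saying whether these are participants randomised or retained. Someone who read only Aim 1 and the power tables could stop randomising at 140. With the plan's own 30% loss, power would then fall below 80% for the primary endpoint and lower still for the Tower of London.
2. The power is tied to participants who reach Visit 4 (Week 4), yet treatment runs for eight weeks and a Week 8 contrast is also planned. If more participants leave after Week 4, the 90% is not shown for Week 8.
3. The power summary computes a difference between arms but closes by calling it an improvement, which could be taken for a within-arm change.

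**Working it through.** **Inputs from the documents.** Difference 7 points (40.7 − 33.7), SD 12.5 in each arm, two-sided alpha 0.05, 70 per arm, drop-out 30%.

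**Step 1: reproduce the plan's figures.** For n per arm, the two-sample t-test has noncentrality 7 / (12.5 × √(2/n)) on 2n − 2 degrees of freedom.

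- n = 70: 7 / (12.5 × 0.1690) = 3.313, power 0.9082. The plan states 0.90822, and the other ten rows of its table also match. A one-sided test would give 0.951, so the table is two-sided, as its summary says.
- Number to randomise: 140 / (1 − 0.30) = 200, as stated.

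**Step 2: Aim 1 read literally.** 140 × 0.70 = 98, or 49 per arm.

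| Endpoint | 70 per arm | 49 per arm |
|---|---|---|
| SF-36 Physical Component (7, SD 12.5) | 90.8% | 78.4% |
| Tower of London (0.44, SD 0.84) | 86.8% (plan: 86%) | 72.8% |
| Pain (0.6, SD 1.0) | 94.1% (plan: 94%) | 83.6% |

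The right-hand column needs 140 randomised together with a 30% loss. No section combines the two. The only place that states the 30% also raises the number randomised to about 200.

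**Step 3: Week 8 by simple t-test.** The documents give no loss after Week 4, so the further losses below are assumptions.

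| Assumed further loss | Per arm at Week 8 | Power |
|---|---|---|
| None (30% is whole-study loss) | 70 | 90.8% |
| 5% | 66 (66.5 rounded down) | 89.1% |
| 10% | 63 | 87.7% |
| 20% | 56 | 83.6% |

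Power is still 80.7% at 52 per arm, which is a further loss of 1 − 52/70 = 25.7%.

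**Step 4: Week 8 under the planned type of model.** Take AR(1) correlation r between adjacent visits, baseline as covariate, loss at random, 70 per arm at Week 4 and 63 at Week 8. The variance of one arm's adjusted Week 8 mean is

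12.5² × [(1 − r²)/63 + r²(1 − r²)/70].

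The plan gives no correlation for the SF-36, so r = 0.30 and 0.50 are assumed.

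- r = 0.30: 156.25 × (0.014444 + 0.001170) = 2.440. The standard error of the difference is √(2 × 2.440) = 2.209, the ratio is 7/2.209 = 3.169, and power is 88.2% (88.7% by normal approximation).
- r = 0.50: 156.25 × (0.011905 + 0.002679) = 2.279. The standard error is 2.135, the ratio is 3.279, and power is 90.2% (90.6% by normal approximation).

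Equal correlation between all visits would give about 91% and 95%, but AR(1) is the plan's default, so the lower pair is the fairer guide.

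**Step 5: margin in the SD.** With the cited SD of 7.5, even 49 per arm gives 99.6%.

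**The case for a change.** The strongest case for a change is that the number randomised and the visit covered by the power claim are basic design facts, and that aligning them costs a few words. Aim 1 does use the word randomised for 140, and that is literally inconsistent with about 200. Week 8 is not incidental either: it is the only efficacy assessment after the last step of the titration schedule. Withdrawals can occur after Week 4, and the simple comparison drops below 90% once 3 per arm are lost (68 per arm gives 90.0%, 67 gives 89.6%).

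The literal mismatch in Aim 1 stands, as does the missing time window for the 30%. Neither changes the trial. Subject Recruitment shows how 140 and 200 relate and names the population behind the power analysis, so the operational target is not in doubt.

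Nor does the text force a Week 4 reading of the 90%. The power section names no visit. Visit 4 is the first SF-36 assessment after randomisation (Study Timeline, item 9), so reaching it gives a participant one post-baseline value for the mixed model. The 140 can fairly be read as an evaluable count. Restating the headline power as a Week 4 comparison would add a restriction that the plan does not make, since it tests both weeks.

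The closing word about improvement is also harmless: the sentence before it gives the two group means being compared.

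**Conclusion.** No change to the plan follows. The mismatch in Aim 1 is a clerical slip that Subject Recruitment resolves: randomise about 200 so that 140 reach Visit 4. The stated 90% is correct at 70 per arm, and the 78.4% describes a trial that the plan does not propose.

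The Week 8 point is missing detail of small size. Power there is 90.8% if the 30% is whole-study loss. By simple t-test it is about 88% to 89% for an assumed further loss of 5% to 10%. Under AR(1), after 10% further loss, it is about 88% to 90%. These figures rest on the plan's 7-point difference and SD of 12.5, on loss at random, and on assumed adjacent-visit correlations of 0.30 to 0.50. The gap is therefore at most about 3 points for losses in that range, with an SD already set well above the cited 7.5. Recruitment, the model fitted and the reading of the result would be the same either way.
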